7.2. Adverse Event Characteristics

CTCAE term (AE description) and grade: The descriptions and grading scales found in the revised NCI Common Terminology Criteria for Adverse Events (CTCAE) version 5.0 will be utilized for AE reporting. All appropriate treatment areas should have access to a copy of the CTCAE version 5.0.

- CTCAE v5.0 documents, including a mapping document, are available on the CTEP website: https://ctep.cancer.gov/protocolDevelopment/electronic_applications/ctc.htm
- **‘Expectedness’:** AEs can be ‘Unexpected’ or ‘Expected’ (see Section 7.1 above) for expedited reporting purposes only. ‘Expected’ AEs (the ASAEL) are ***bold and italicized*** in the CAEPR (Section 7.1.1).
- **Attribution** of the AE:
 - Definite – The AE *is clearly related* to the study treatment.
 - Probable – The AE *is likely related* to the study treatment.
 - Possible – The AE *may be related* to the study treatment.
 - Unlikely – The AE *is doubtfully related* to the study treatment.
 - Unrelated – The AE *is clearly NOT related* to the study treatment.

7.3. Expedited Adverse Event Reporting

7.3.1. Expedited AE reporting for this study must use CTEP-AERS (Adverse Event Expedited Reporting System), accessed via the CTEP home page (<http://ctep.cancer.gov>). The reporting procedures to be followed are presented in the “CTEP, NCI Guidelines: Adverse Event Reporting Requirements” which can be downloaded from the CTEP home page (<http://ctep.cancer.gov>). These requirements are briefly outlined in the table below (Section 7.3.3).

In the rare occurrence when Internet connectivity is disrupted a 24-hour notification is to be made to NCI by telephone at [contact]. An electronic report **MUST** be submitted immediately upon reestablishment of internet connection. Please note that all paper CTEP-AERS forms have been removed from the CTEP website.

7.3.2. CTEP-AERS is programmed for automatic electronic distribution of reports to the following individuals: Study Coordinator of the Lead Organization, Principal Investigator, and the local treating physician. CTEP-AERS provides a copy feature for other e-mail recipients.

7.4. Expedited Reporting Guidelines

7.4.1. CTEP-AERS Reporting Requirements for Adverse Events That Occur Within 30 Days¹ of the Last Dose of the Investigational Agent on Phase 1 Trials

Phase 1 Trials								
	Grade 1	Grade 2	Grade 2	Grade 3		Grade 3		Grades 4 & 5 ^{2,3}
	Unexpected and Expected	Unexpected	Expected	Unexpected with Hospitalization	Unexpected without Hospitalization	Expected with Hospitalization	Expected without Hospitalization	Unexpected and Expected
Unrelated Unlikely	Not Required	Not Required	Not Required	10 Calendar Days	Not Required	10 Calendar Days	Not Required	24-Hour; 5 Calendar Days
Possible Probable Definite	Not Required	10 Calendar Days	Not Required	24-Hour; 5 Calendar Days	24-Hour; 5 Calendar Days	10 Calendar Days	Not Required	24-Hour; 5 Calendar Days

¹ Adverse events with attribution of possible, probable, or definite that occur **greater than 30 days** after the last dose of treatment with an agent under a CTEP IND require reporting as follows:
 CTEP-AERS 24-hour notification followed by complete report within 5 calendar days for:

- Grade 3 unexpected events with hospitalization or prolongation of hospitalization
- Grade 4 unexpected events
- Grade 5 expected events and unexpected events

1. Although an CTEP-AERS 24-hour notification is not required for death clearly related to progressive disease, a full report is required as outlined in the table.

³ Pregnancy is Grade 4/5 unexpected event.

December 15, 2004

Note: All deaths on study require both routine and expedited reporting regardless of causality. Attribution to treatment or other cause must be provided.

- Expedited AE reporting timelines defined:
 - “24 hours; 5 calendar days” – The investigator must initially report the AE via CTEP-AERS within 24 hours of learning of the event followed by a complete CTEP-AERS report within 5 calendar days of the initial 24-hour report.
 - “10 calendar days” - A complete CTEP-AERS report on the AE must be submitted within 10 calendar days of the investigator learning of the event.
- Any medical event equivalent to CTCAE grade 3, 4, or 5 that precipitates hospitalization (or prolongation of existing hospitalization) must be reported regardless of attribution and designation as expected or unexpected with the exception of any events identified as protocol-specific expedited adverse event reporting exclusions.
- Any event that results in persistent or significant disabilities/incapacities, congenital anomalies, or birth defects must be reported via CTEP-AERS if the event occurs following treatment with an agent under a CTEP IND.

- Pregnancy (Grade 4/5 unexpected event) must be reported within 24 hour of learning of the event. This applies to patients on cediranib alone or cediranib and lenalidomide.

For patients who become pregnant while on cediranib alone. Discontinue cediranib immediately. The Investigator will follow the subject until completion of the pregnancy, and must notify CTEP-AERS reporting system of the outcome as specified below. The Investigator will provide this information as a follow-up to the initial SAE. All neonatal deaths that occur within 30 days of birth should be reported, without regard to causality, as SAEs. In addition, any infant death after 30 days that the Investigator suspects is related to the *in utero* exposure to cediranib should also be reported.

Females of Childbearing Potential:

- Pregnancies and suspected pregnancies (including a positive pregnancy test regardless of age or disease state) of a female subject or the partner of a male subject occurring while the subject is on lenalidomide or within 28 days after the subject's last dose, are considered immediately reportable events. Lenalidomide is to be discontinued immediately. The pregnancy, suspected pregnancy, or positive pregnancy test must be reported via CTEP-AERS as a **grade 4** event under: SOC pregnancy, puerperium and perinatal conditions; adverse event: **pregnancy, puerperium and perinatal conditions-other, fetal exposure.**
 - *The female subject should be referred to an obstetrician-gynecologist, preferably one experienced in reproductive toxicity for further evaluation and counseling.*
- The Investigator will follow the female subject until completion of the pregnancy, and must make an amendment to the initial pregnancy report immediately regarding the outcome of the pregnancy and neonatal status (either normal or abnormal outcome).
- If the outcome of the pregnancy was abnormal (including spontaneous or therapeutic abortion, fetal demise and congenital abnormalities), the Investigator should report the abnormal outcome as an amendment to the initial pregnancy report as soon as the as the Investigator has knowledge of the outcome.
- All neonatal deaths and neonatal complications that occur within 28 days of birth should be reported, without regard to causality, as an amendment to the initial pregnancy report. In addition, any infant death after 28 days that the Investigator suspects is related to the *in utero* exposure to the lenalidomide should also be reported as an amendment within 24 hours of the Investigator's knowledge of the event.

Male Subjects

- If a female partner of a male subject taking investigational product becomes pregnant, the male subject taking lenalidomide should notify the Investigator, and the pregnant female partner should be advised to call her healthcare provider

immediately.

7.4.2. CTEP-AERS Reporting Requirements for Adverse Events That Occur Within 30 Days¹ of the Last Dose of the Investigational Agent on Phase 2 and 3 Trials

Phase 2 and 3 Trials									
	Grade 1	Grade 2	Grade 2	Grade 3		Grade 3		Grades 4 & 5 ²	Grades 4 & 5 ^{2,3}
	Unexpected and Expected	Unexpected	Expected	Unexpected with Hospitalization	Unexpected without Hospitalization	Expected with Hospitalization	Expected without Hospitalization	Unexpected	Expected
Unrelated Unlikely	Not Required	Not Required	Not Required	10 Calendar Days	Not Required	10 Calendar Days	Not Required	10 Calendar Days	10 Calendar Days
Possible Probable Definite	Not Required	10 Calendar Days	Not Required	10 Calendar Days	10 Calendar Days	10 Calendar Days	Not Required	24-Hour; 5 Calendar Days	10 Calendar Days

¹ Adverse events with attribution of possible, probable, or definite that occur **greater than 30 days** after the last dose of treatment with an agent under a CTEP IND require reporting as follows:
 CTEP-AERS 24-hour notification followed by complete report within 5 calendar days for:
 • Grade 4 and Grade 5 unexpected events
 CTEP-AERS 10 calendar day report:
 • Grade 3 unexpected events with hospitalization or prolongation of hospitalization
 • Grade 5 expected events
² Although an CTEP-AERS 24-hour notification is not required for death clearly related to progressive disease, a full report is required as outlined in the table.
³ Pregnancy is Grade 4/5 unexpected event.

December 15, 2004

Note: All deaths on study require both routine and expedited reporting regardless of causality. Attribution to treatment or other cause must be provided.

- Expedited AE reporting timelines defined:
 - “24 hours; 5 calendar days” – The investigator must initially report the AE via CTEP-AERS within 24 hours of learning of the event followed by a complete CTEP-AERS report within 5 calendar days of the initial 24-hour report.
 - “10 calendar days” - A complete CTEP-AERS report on the AE must be submitted within 10 calendar days of the investigator learning of the event.
- Any medical event equivalent to CTCAE grade 3, 4, or 5 that precipitates hospitalization (or prolongation of existing hospitalization) must be reported regardless of attribution and designation as expected or unexpected with the exception of any events identified as protocol-specific expedited adverse event reporting exclusions.

- Any event that results in persistent or significant disabilities/incapacities, congenital anomalies, or birth defects must be reported via CTEP-AERS if the event occurs following treatment with an agent under a CTEP IND.
- Use the NCI protocol number and the protocol-specific patient ID assigned during trial registration on all reports.
- Pregnancy (Grade 4/5 unexpected event) must be reported within 24 hour of learning of the event. This includes pregnancies while on cediranib or lenalidomide or within 4 weeks after a subjects last dose of cediranib or lenalidomide.

For patients who become pregnant while on cediranib alone. Discontinue cediranib immediately. The Investigator will follow the subject until completion of the pregnancy, and must notify CTEP-AERS reporting system of the outcome as specified below. The Investigator will provide this information as a follow-up to the initial SAE. All neonatal deaths that occur within 30 days of birth should be reported, without regard to causality, as SAEs. In addition, any infant death after 30 days that the Investigator suspects is related to the *in utero* exposure to cediranib should also be reported.

Females of Childbearing Potential:

- Pregnancies and suspected pregnancies (including a positive pregnancy test regardless of age or disease state) of a female subject or the partner of a male subject occurring while the subject is on lenalidomide or within 28 days after the subject's last dose, are considered immediately reportable events. Lenalidomide is to be discontinued immediately. The pregnancy, suspected pregnancy, or positive pregnancy test must be reported via CTEP-AERS as a **grade 4** event under: SOC pregnancy, puerperium and perinatal conditions; adverse event: **pregnancy, puerperium and perinatal conditions-other, fetal exposure.**
 - *The female subject should be referred to an obstetrician-gynecologist, preferably one experienced in reproductive toxicity for further evaluation and counseling.*
- The Investigator will follow the female subject until completion of the pregnancy, and must make an amendment to the initial pregnancy report immediately regarding the outcome of the pregnancy and neonatal status (either normal or abnormal outcome).
- If the outcome of the pregnancy was abnormal (including spontaneous or therapeutic abortion, fetal demise and congenital abnormalities), the Investigator should report the abnormal outcome as an amendment to the initial pregnancy report as soon as the as the Investigator has knowledge of the outcome.
- All neonatal deaths and neonatal complications that occur within 28 days of birth should be reported, without regard to causality, as an amendment to the initial pregnancy report. In addition, any infant death after 28 days that the Investigator

suspects is related to the *in utero* exposure to the lenalidomide should also be reported as an amendment within 24 hours of the Investigator's knowledge of the event.

Male Subjects

- If a female partner of a male subject taking investigational product becomes pregnant, the male subject taking lenalidomide should notify the Investigator, and the pregnant female partner should be advised to call her healthcare provider immediately.

7.5. Routine Adverse Event Reporting

All Adverse Events **must** be reported in routine study data submissions. **AEs reported through CTEP-AERS must also be reported in routine study data submissions.**

7.6. Secondary Malignancies (including AML and MDS)

Investigators are required to report cases of secondary malignancies, including AML/MDS, occurring on or following treatment on NCI-sponsored chemotherapy protocols via CTEP-AERS with CTCAE 5.0. Refer to the CTEP web site (<http://ctep.cancer.gov>) for additional information about secondary AML/MDS reporting.

- In addition to all routine AE reporting mechanisms and any Cooperative Group-specific second/secondary malignancy reporting requirements, all new malignant tumors must be reported through CTEP-AERS whether or not they are thought to be related to either previous or current treatment. All new malignancies should be reported including solid tumors (including non-melanoma skin malignancies), hematologic malignancies, Myelodysplastic Syndrome (MDS)/Acute Myelogenous Leukemia (AML), and *in situ* tumors.
- Using CTCAE v5.0, the event(s) may be reported as one of the following: (1) Leukemia secondary to oncology chemotherapy; (2) Myelodysplastic syndrome; (3) Treatment-related secondary malignancy; or (4) Neoplasm other, malignant (grade 3 or 4).
- These events should be reported for the duration of the study treatment and during any protocol-specified follow-up periods. Refer to the "CTEP website <http://ctep.cancer.gov>) for additional information about secondary AML/MDS reporting.

8. PHARMACEUTICAL INFORMATION

A list of the adverse events and potential risks associated with the investigational or

commercial agents administered in this study can be found in Section 7.1.

8.1. CTEP-Supplied Investigational Agents

8.1.1. Cediranib (AZD2171, NSC 732208)

Chemical Name: 4-[(4-Fluoro-2-methyl-1H-indol-5-yl)oxy]-6-methoxy-7-[3-(pyrrolidin-1-yl)propoxy] quinazoline maleate

Other Names: cediranib, AZD2171 maleate

CAS Registry Number: 288383-20-0 (for the free base)

Molecular Formula: C₂₅H₂₇FN₄O₃ · C₄H₄O₄ **M W:** 566.59 (maleate salt), 450.52 (free base)

Approximate Solubility: The aqueous solubility of AZD2171 (cediranib) is 0.0006 mg/mL for the free base (distilled water, pH 8.1 at 25°C) and 1.76 mg/mL for the maleate salt (distilled water, at 25°C).

Mode of Action: AZD2171 (cediranib) is a highly potent tyrosine kinase inhibitor of all three vascular endothelial growth factor receptors (VEGFR-1, -2 and -3). Inhibition of VEGF signaling leads to inhibition of angiogenesis, neovascular survival and vascular permeability. Pre-clinical tumor models show that AZD2171 (cediranib) reduces micro-vessel density and metastasis, indicating that it limits tumor growth.

How Supplied: Astra-Zeneca supplies and CTEP, NCI, DCTD distributes AZD2171 (cediranib). The agent is available as beige, round, biconvex, film-coated tablets containing 15 mg, and 20 mg of AZD2171 (cediranib) free base. The 15 mg and 20 mg tablets are 7 mm and 8 mm in diameter, respectively. Each high-density polyethylene bottle contains 35 tablets.

Tablet excipients include mannitol, dibasic calcium phosphate anhydrous, sodium starch glycolate, microcrystalline cellulose, and magnesium stearate with a film coat containing hypromellose 2910, polyethylene glycol 400, red iron oxide, yellow iron oxide, black iron oxide, and titanium dioxide.

Storage: Store intact bottles at controlled room temperature 20°C to 25°C (68 to 77°F) and protect from light and moisture.

Stability: Stability studies are ongoing. Dispense AZD2171 (cediranib) tablets in their original containers. Alternatively, if exact quantity is dispensed in a pharmacy bottle, the supply should be assigned a 30-day expiration.

If a storage temperature excursion is identified, promptly return AZD2171 (cediranib) to room temperature and quarantine the supplies. Provide a detailed report of the excursion (including documentation of temperature monitoring and duration of the excursion) to [contact] for determination of suitability.

Route and Method of Administration: Oral. AZD2171 (cediranib) tablets should be taken either one hour before or two hours after meals.

If the study sponsor determines appropriate, cediranib tablets may be administered as a dispersion in plain water. Liquids other than non-carbonated water should not be used and the tablets should not be crushed or ground. The following procedure is recommended by the manufacturer for patients who can swallow liquids:

Drop the appropriate dose of cediranib tablet/s into a glass containing 50-60 mL non-carbonated water. Stir the tablet/s until dispersed in the water, about 10 minutes (no crushing). Swallow the liquid immediately after dispersion is completed. Any residue in the glass is mixed with a half glass of water and swallowed.

The manufacturer recommends the following for naso-gastric or gastrostomy tube administration:

Follow the dispersion instructions above. Administer the dispersion using polyurethane or PVC naso-gastric, naso-intestinal or percutaneous endoscopic gastrostomy feeding systems in conjunction with polyurethane syringes. PVC syringes are not recommended. Conduct two system washes to ensure the patient receives the full dose.

Potential Drug Interactions: AZD2171 (cediranib) is primarily metabolized by flavin-containing monooxygenase enzymes (FMO1 and FMO3) and UGT1A4. It is not a substrate of CYP450 enzymes. In vitro studies suggest that AZD2171 (cediranib) is a substrate for P-glycoprotein (Pgp), but not breast cancer resistance protein (BCRP). Since clinically relevant induction or inhibition of FMO enzymes is uncommon, use caution in patients taking concomitant medications that are strong inhibitors (e.g. ketoconazole) or strong inducers (e.g. rifampicin, carbamazepine, phenobarbital, phenytoin and St. John's Wort) of UGT1A4 or Pgp in particular. If chronic concomitant administration of strong inducers or inhibitors is unavoidable, consult the protocol document and/or the principal investigator before making any dose adjustments.

In vitro studies show that AZD2171 (cediranib) did not inhibit CYP 1A2, 2A6, 2C8, 2C9, 2C19 and 2E1 and showed no induction of CYP 1A2, 2B6 and 3A4/5. It did weakly inhibit CYP 2D6 and 3A4/5, but this inhibition not expected to cause any clinically relevant drug interactions.

In vitro studies show that AZD2171 (cediranib) is a weak inhibitor of BCRP, but not Pgp. Use caution in patients who are taking concomitant medications that are sensitive substrates of BCRP transporters since there is a potential for drug-drug interactions.

AZD2171 (cediranib) is approximately 95% bound to human plasma proteins, with human serum albumin and α 1-acid glycoprotein accounting for most of this binding. Use caution in patients taking concomitant medications with narrow therapeutic ranges that are also highly protein-bound.

Oral anticoagulants are not absolutely contraindicated during treatment with AZD2171 (cediranib); however, use AZD2171 (cediranib) with caution and increase monitoring in patients while on study. Patients who receive VEGF inhibitors are at increased risk of bleeding and hemorrhage.

Patient Care Implications: Agents that inhibit VEGF signaling have the potential to affect wound healing. For patients already enrolled onto the protocol, the manufacturer recommends holding AZD2171 (cediranib) for 2 weeks prior to elective surgery and restarting when the surgical wound is healed. Protocol exclusion criteria should include patients who have had major thoracic or abdominal surgery within 2 weeks prior to start of study or patients with any surgical incision that is not fully healed.

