3.2. Exclusion Criteria

3.2.1. Patients who have had chemotherapy or radiotherapy within 4 weeks (6 weeks for nitrosoureas or mitomycin C) prior to entering the study or those who have not recovered from adverse events due to agents administered more than 4 weeks earlier. At least 4 weeks must have elapsed since any major surgery. Patients with prior use of thalidomide or lenalidomide are excluded.

3.2.2. Patients may not be receiving any other investigational agents.

3.2.3. Patients with known brain metastases should be excluded because of their poor prognosis and because they often develop progressive neurologic

dysfunction that would confound the evaluation of neurologic and other adverse events. N.B.: Patients with brain metastases with stable neurologic status following local therapy (surgery or radiation) for at least 8 weeks from definitive therapy and without neurologic dysfunction that would confound the evaluation of neurologic and other adverse events are eligible for participation.

- 3.2.4. History of allergic reactions attributed to compounds of similar chemical or biologic composition to cediranib or lenalidomide or other agents used in the study.
- 3.2.5. Patients with poorly controlled hypertension (systolic blood pressure of 140 mmHg or higher or diastolic blood pressure of 90 mmHg or higher) are ineligible.
- 3.2.6. Patients with 1+ proteinuria or greater on urinalysis should collect a 24 hour urine collection. Patients with greater than 1.5 gram protein/ 24 hours are excluded.
- 3.2.7. Because lenalidomide may increase the risk of DVT or PE, patients must stop Epopen at least 4 weeks prior to enrollment.
- 3.2.8. Patients with any condition (e.g., gastrointestinal tract disease resulting in malabsorption, prior surgical procedures affecting absorption, or active peptic ulcer disease) that impairs their ability to absorb cediranib tablets or lenalidomide capsules are excluded. However, for patients who are unable to swallow cediranib tablets, cediranib tablets may be administered as a dispersion in water (ie, either drinking water, sterile water [for injection] or purified water). Cediranib can be administered via nasogastric tube or gastostomy tube. See section 5.1 for recommended procedure. For patients unable to swallow lenalidomide whole, lenalidomide can be administered via gastostomy feeding tube following the instructions in Appendix M.
- 3.2.9. Patients with any of the following conditions are excluded:

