- Serious or non-healing wound, ulcer, or bone fracture.
 - History of abdominal fistula, gastrointestinal perforation, or intra-abdominal abscess within 28 days of treatment.
 - Any history of cerebrovascular accident (CVA) or transient ischemic attack within 12 months prior to study entry.
 - History of myocardial infarction, cardiac arrhythmia, stable/unstable angina, symptomatic congestive heart failure, or coronary/peripheral artery bypass graft or stenting within 12 months prior to study entry.
 - History of pulmonary embolism within the past 12 months.
 - Class III or IV heart failure as defined by the NYHA functional classification system (see Appendix G).

- 3.2.10. Patients with uncontrolled intercurrent illness including, but not limited to, ongoing or active infections or psychiatric illness/social situations that would limit compliance with study requirements are ineligible.
- 3.2.11. Pregnant women are excluded from this study because cediranib and lenalidomide are agents with the potential for teratogenic or abortifacient effects. Because there is an unknown but potential risk for adverse events in nursing infants secondary to treatment of the mother with cediranib or lenalidomide, breastfeeding should be discontinued if the mother is treated with cediranib with or without lenalidomide.
- 3.2.12. HIV-positive patients on combination antiretroviral therapy are ineligible because of the potential for pharmacokinetic interactions with cediranib or cediranib with lenalidomide. In addition, these patients are at increased risk of lethal infections when treated with marrow-suppressive therapy. Appropriate studies will be undertaken in patients receiving combination antiretroviral therapy when indicated.

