		Hepatic failure	
INFECTIONS AND INFESTATIONS			
	Infection ⁴		
INJURY, POISONING AND PROCEDURAL COMPLICATIONS			
		Wound complication	
INVESTIGATIONS			
	Alanine aminotransferase increased		Alanine aminotransferase increased (Gr 3)
	Alkaline phosphatase increased		
	Aspartate aminotransferase increased		Aspartate aminotransferase increased (Gr 3)
	Lymphocyte count decreased		

Adverse Events with Possible Relationship to Cediranib (AZD2171) (CTCAE 5.0 Term) [n= 1608]			Specific Protocol Exceptions to Expedited Reporting (SPEER)
Likely (>20%)	Less Likely (<=20%)	Rare but Serious (<3%)	
	Neutrophil count decreased		
	Platelet count decreased		
	Thyroid stimulating hormone increased		Thyroid stimulating hormone increased (Gr 2)
	Weight loss		Weight loss (Gr 2)
METABOLISM AND NUTRITION DISORDERS			
Anorexia			Anorexia (Gr 3)
	Dehydration		Dehydration (Gr 3)
	Hypophosphatemia		Hypophosphatemia (Gr 3)
MUSCULOSKELETAL AND CONNECTIVE TISSUE DISORDERS			
	Generalized muscle weakness		
NERVOUS SYSTEM DISORDERS			
	Dizziness		Dizziness (Gr 2)
	Headache		Headache (Gr 3)
	Lethargy		
		Leukoencephalopathy	
		Reversible posterior leukoencephalopathy syndrome	
RENAL AND URINARY DISORDERS			
		Nephrotic syndrome	
	Proteinuria		Proteinuria (Gr 2)
RESPIRATORY, THORACIC AND MEDIASTINAL DISORDERS			
	Cough		Cough (Gr 2)
	Dyspnea		Dyspnea (Gr 3)
	Laryngeal mucositis		Laryngeal mucositis (Gr 2)
	Pharyngeal mucositis		Pharyngeal mucositis (Gr 2)
	Tracheal mucositis		Tracheal mucositis (Gr 2)
Voice alteration			Voice alteration (Gr 2)
SKIN AND SUBCUTANEOUS TISSUE DISORDERS			
	Palmar-plantar erythrodysesthesia syndrome		Palmar-plantar erythrodysesthesia syndrome (Gr 2)
VASCULAR DISORDERS			
		Arterial thromboembolism	
Hypertension			Hypertension (Gr 3)
	Thromboembolic event		Thromboembolic event (Gr 4)
	Vascular disorders - Other (hemorrhage) ⁵		

¹This table will be updated as the toxicity profile of the agent is revised. Updates will be distributed to all Principal Investigators at the time of revision. The current version can be obtained by contacting [contact]. Your name, the name of the investigator, the protocol and the agent should be included in the e-mail.

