10. STUDY CALENDAR

Baseline evaluations are to be conducted within 2 week prior to start of protocol therapy. Scans and x-rays must be done □4 weeks prior to the start of therapy. In the event that the patient's condition is deteriorating, laboratory evaluations should be repeated within 48 hours prior to initiation of the next cycle of therapy.

	Pre-Study ^k	Day 1	Day 8	Day 15	Day 22	Day 29	Day 36	Day 43	Day 50	Day 57	Day 64	Day 71	Day 78	Day 85	Day 113	Off Study ^k
Cediranib^a																
Lenalidomide^b																
Anticoagulation ^c																
Informed consent	X															
Demographics	X															
Medical history	X															
ECHO/MUGA ^o	X															
Physical exam ⁿ	X	X		X		X		X		X				X	X	X
Vital signs ⁿ	X	X		X		X		X		X				X	X	X
Height	X															
Weight ⁿ	X	X		X		X		X		X				X	X	X
Performance status ⁿ	X	X		X		X		X		X				X	X	X
CBC w/diff, plts ⁿ	X	X		X		X		X		X		X		X	X	X
Serum chemistry ^{d,n}	X	X		X		X		X		X		X		X	X	X
Blood pressure measurement ^e	X	X	X	X	X	X		X		X		X		X	X	X

EKG	X															
Urinalysis ^{i,n}	X	X				X				X			X	X	X	
B-HCG	X ^{f,g}	X ^{f,g}	X ^{f,g}	X ^{f,g}	X ^{f,g}	X ^{f,g}			X ^{f,g}	X ^{f,g}		X ^{f,g}	X ^{f,g}	X ^{f,g}	X ^{f,g}	
Patient Education and counseling ^h	X ^h	X ^h				X ^h			X ^h			X ^h	X ^h	X ^h	X ^h	
TSH	X								X ^m							X
Throglobulin	X								X ^m							X
Radiology studies ^l	X								X							X
Archival tissue for correlative studies ^j	X															

- a: **Cediranib:** Dose as assigned; *administration schedule*
- b: **Lenalidomide:** Dose as assigned, only enough lenalidomide for 28 days or one cycle of study treatment (whichever is shorter) may be provided to the patient each cycle; *administration schedule*
- c: Anticoagulation: All patients receiving lenalidomide should receive prophylactic anti-coagulation. Aspirin (81 or 325 mg) is the recommended agent for anti-coagulation prophylaxis. Low molecular weight heparin may be utilized in patients that are intolerant to ASA. Coumadin should be used with caution and close monitoring of INR.
- d: Albumin, alkaline phosphatase, total bilirubin, bicarbonate, BUN, calcium, chloride, creatinine, glucose, phosphorus, potassium, total protein, SGOT [AST], SGPT [ALT], sodium.
- e: Blood pressure measurement may be performed more frequently as dictated by clinical observations. See Appendix D for blood pressure measurement guidelines.

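### Section 8.1.1 says an incompletely healed surgical incision should be an exclusion, but Section 3.2 does not reach a recent minor-procedure incision that is healing normally

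*Combined protocol and SAP*

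**What the plan says.** Under Patient Care Implications, Section 8.1.1 opens with the reason for caution: "Agents that inhibit VEGF signaling have the potential to affect wound healing". For patients already on study it reports the manufacturer's advice to stop cediranib 2 weeks ahead of elective surgery and to resume once the wound has healed. It then turns to entry, and begins with recent operations: "Protocol exclusion criteria should include patients who have had major thoracic or abdominal surgery". The rest of that sentence gives the time window and adds a second group, defined by the state of the incision: "within 2 weeks prior to start of study or patients with any surgical incision that is not fully healed".

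Two items in Section 3.2 bear on this. Section 3.2.1 states: "At least 4 weeks must have elapsed since any major surgery". Section 3.2.9 lists among its excluded conditions: "Serious or non-healing wound, ulcer, or bone fracture".

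The cediranib risk list in Section 7.1.1 has "Wound complication" in its rare-but-serious column (below 3%).

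**The concern.** Section 8.1.1 names two groups that the exclusion list should cover, and Section 3.2 fully covers only one. Sites register patients against Section 3, not against the pharmacy monograph. Where the two differ, Section 3 decides who enters.

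The patient in question had a minor procedure, such as an excision biopsy, shortly before starting cediranib, and the incision is closing as expected. The drug section would have that patient wait. No criterion in Section 3 does. An enrolled patient who has elective surgery is advised to wait for healing before resuming the drug, so the same paragraph already treats healing as the condition for dosing. What is at stake is an avoidable wound complication in a small group. No analysis or error rate is affected.

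**Working it through.** No power or error-rate calculation applies. The check compares the 8.1.1 advice with the criteria in Sections 3.1 and 3.2.

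| Situation at entry | Section 8.1.1 | Section 3 | Covered? |
|---|---|---|---|
| Major thoracic or abdominal surgery | 2 weeks = 14 days | 3.2.1: 4 weeks = 28 days, any site | Yes, more strictly |
| Serious or non-healing wound after any procedure | Exclude if the incision is not healed | 3.2.9 | Yes |
| Minor-procedure incision, recent, healing normally | Exclude until healed | None | No |

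**Row 1.** 28 / 14 = 2. The protocol's interval is twice the advised one and applies to every surgical site. A reader comparing 14 with 28 days should see a stricter rule, not a conflict.

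**Row 2.** A patient more than 28 days past major surgery whose incision is still open may already count as having a non-healing wound. That patient is not counted in the gap.

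**Row 3.** The advice in 8.1.1 turns on whether healing is complete. The criterion in 3.2.9 turns on whether healing has failed or the wound is serious. An incision about a week old that is closing normally fails the 8.1.1 test and passes the 3.2.9 test. Two other items might seem to help but do not. The recovery clause in 3.2.1 concerns adverse events from earlier agents, not procedures. Section 3.2.10 concerns uncontrolled intercurrent illness.

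**Does the trial create such incisions?** No. Section 9 and Study Calendar note j use archival tissue, so any incision comes from ordinary care.

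**Could it be seen?** Yes. The calendar has a physical exam pre-study and on Day 1, and "Baseline evaluations are to be conducted within 2 week prior to start of protocol therapy". The occasion exists, but no criterion says what to do with the finding. Section 4.1 asks for treatment to begin within 14 days of registration, so waiting is not the default.

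**Timing.** Lenalidomide was stopped on Arm B on April 10, 2015 (Schema, Section 5.1.2). The protocol history dates the cediranib monograph update (Amendment 26) to July 7, 2016. April 10, 2015 to April 10, 2016 is 366 days, and from there to July 7 is 88 days: 366 + 88 = 454 days, and 454 / 30.44 = 14.9 months. The documents do not say whether the incision sentence was new in that update. If it was, the mismatch began only after the combination arm had lost its second drug.

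**The case against.** The case for leaving the text alone is a fair one.

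- **The main hazard is already controlled.** Section 3.2.1 is longer and broader than the advice, and 3.2.9 removes serious and non-healing wounds. This stands, and it is why the point is minor.
- **The 8.1.1 sentence is advice on writing the criteria, not a criterion.** This also stands. A reader might infer that the protocol holds two competing eligibility rules. It does not: Section 3 governs, and 8.1.1 says what Section 3 should contain. The gap is an item of advice carried over only in part.
- **Section 3.2 sets no waiting period after a minor procedure.** A reader might count this as a second fault. The documents do not support that. The only interval in the 8.1.1 entry advice concerns major thoracic or abdominal surgery; for other incisions it asks about healing, not elapsed time.
- **An investigator has the warning and the exam.** True, since 8.1.1 sits in the protocol that each site holds. But a warning in the drug section leaves the decision to the individual investigator.
- **No harm is shown.** Correct. The risk list does not break wound complications down by type of incision, and no count of affected patients is given.
- **The question may be moot.** The 2015 lenalidomide stop suggests that randomised accrual had ended, and the later logged amendments deal largely with risk lists, the monograph and administration. No closure date is stated, so this remains an inference. It limits the practical value of the change but does not remove the difference in wording.

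**Conclusion.** The point holds in a narrow form. The advice in 8.1.1 to exclude patients with an incompletely healed incision is not fully carried into Section 3.2, and the group left uncovered is patients with a recent, normally healing incision from a minor procedure. It is a low-severity safety point and a cheap improvement.

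Its size cannot be calculated from the documents. The number of patients is unknown, probably small, and zero if enrolment has closed. The conclusion assumes that non-healing in 3.2.9 carries its ordinary meaning of a wound that fails to close. A site that reads it as any wound not yet closed would have no gap.

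A reader might go further and conclude that patients were exposed to a known risk, or that recent surgery is poorly controlled. Neither follows. The documents report no such case, may not have contained the sentence during accrual, and control major surgery more tightly than the monograph advises.

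**What to change.** For any patient still to be enrolled, add one item to 3.2.9: *Surgical incision of any kind that has not completely healed (an established, healed gastrostomy or tracheostomy site is allowed).* Leave the 4-week rule in 3.2.1 unchanged, and add no interval for minor procedures.

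The exemption is needed because the protocol admits tube-fed patients. Section 3.2.8 says "Cediranib can be administered via nasogastric tube or gastostomy tube", and Section 5.1 and Appendix M give the procedures. Without it, the new line could be read as excluding patients with a settled stoma. The exemption is a suggestion here; 8.1.1 does not contain it.

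The cost is one line in an amendment. The pre-study and Day 1 exams already on the calendar are enough to apply it, so no visit or test is added. The downside is a short delay for the few patients whose incision is still closing. If enrolment has closed, no change is needed.
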